3.4.2 Secondary Efficacy Endpoints

The secondary efficacy analyses will be performed on the Full Analysis Set.

Analyses of hemodynamic endpoints will be performed using the same ANOVA model as the primary endpoint. Series Plots will be provided for PCWP by position and visit.

Patient global assessment (based on a six-point Likert scale) at Week 6 will be performed by a Mann-Whitney-Wilcoxon test for each of the six symptom's grade. Total score will be calculated as the sum of all 6 scores for the subjects with all 6 scores available.

6MWT exercise distance at Week 6 will be tested using the same ANOVA model as the primary endpoint.

Physician's assessment of New York Heart Association (NYHA) functional class (Class I to IV) will be summarized at each time point by treatment group as a shift table from baseline to post-baseline time point. Percentages will be based on the number of subjects with both a baseline and post-baseline (at the specific time point) assessment. The treatment difference of physician's assessment of functional class at Week 6 will be tested using the two-sided Pearson's chi-squared test.

The incidence of death and hospitalization will be summarized by treatment group. Two-sided 95% CIs for the observed difference in clinical events: death and hospitalizations between the treatment groups will be presented based on a continuity-correct Z-statistic. A by-subjects listing of subjects who died due to any cause will be provided.

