2.2 Study Design

2.2.1 *Overview*

[figure not shown]
This study will be conducted at approximately 20-25 sites in the United States. The Phase 2 study of levosimendan in PH-HFpEF subjects has been designed in two phases (Figure 1). The study will recruit male and female subjects meeting identified enrollment criteria for PH-HFpEF into the lead-in open label phase to identify “responders” to levosimendan intravenous infusion of at 0.10 µg/kg/min for 24 hours \pm 30 min. Subjects that have clinically relevant responses to levosimendan will be randomized to levosimendan or placebo (1:1) and receive intermittent (weekly) study drug infusions (Week 2-5). The first 36 subjects who demonstrate a \geq 4mmHg reduction in PCWP from baseline measured at bicycle exercise (25 watts) with no more than a 10% decrease from baseline in cardiac index will be classified as a “responder” to the

lead-in levosimendan dose and be randomized to the double-blind phase of the study. Patients who do not tolerate the initial levosimendan infusion due to excessive hypotension or tachycardia will be dropped from eligibility. In the double-blinded phase, patients will be randomized to levosimendan or placebo and receive a weekly dose of study drug intravenously at $0.075 \mu\text{g}/\text{kg}/\text{min}$ for 24 hours ± 30 min and if tolerated titrated to $0.10 \mu\text{g}/\text{kg}/\text{min}$ for 24 hours ± 30 min at Week 4. The infusion rate of study drug may be decreased or interrupted as clinically warranted if the subject has hypotension, tachycardia, or signs or symptoms consistent with hypovolemia (e.g., low systolic blood pressure [SBP], decreasing urine output with rising blood urea nitrogen [BUN] and serum creatinine) Record the time of discontinuation or down titration. Patients should be monitored closely until clinically stable. See Protocol Attachment 1 for infusion rates and instructions on dose adjustments. Patients will be evaluated Week 6 to determine the efficacy and safety of levosimendan. Randomized subjects that have not received study drug weekly through Week 5 and returned for evaluation on Week 6 will be replaced to ensure 18 subjects have completed in each study group.

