2.3.2 Secondary Efficacy Endpoints

- Change in Cardiac Index at rest and with exercise at Week 6
- Change in PVR effect at rest and with exercise at Week 6
- Change in PCWP when supine and legs elevated at Week 6
- Change in mean pulmonary artery pressure (mPAP) effect at rest and with exercise at Week 6
- Change in right atrial pressure (RAP) effect at rest and with exercise at Week 6
- Patient global assessment (based on a six-point Likert scale) at Week 6
- 6MWT at Week 6 (distance)
- Physician's Assessment of Functional Class
- Clinical Events: Death and hospitalizations

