3.2.5 Full Analysis Set

The Full Analysis Set is defined as randomized subjects who received any blinded study drug and completed the study with Week 6 office visit.

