3.3 Subject Data and Study Conduct

3.3.1 Subject Disposition

Subjects in each analysis population, as well as subjects who complete the study, and subjects who prematurely discontinue from the study will be summarized by treatment assignments in the double-blind phase using descriptive statistics. In addition, for subjects who prematurely discontinue from the study, the reasons for discontinuation will be summarized by treatment group.

Subjects who discontinue the study prior to the Week 6 office visit will be replaced to ensure 18 randomized subjects in both arms (levosimendan, placebo) have completed the study for the primary analysis. If a subject has been identified for replacement, the Interactive Response Technology (IRT) will select the lowest available randomization number (with the same treatment group as the subject being selected) in the

"Replacement Blocks" section of the randomization schedule for the treatment assignment of the replacement subject. Thus, the treatment assignment of both the subject being replaced and the replacement subject will remain blinded.

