3.4 Efficacy Assessment

All efficacy analyses will be based on the Full Analysis Set and all statistical tests will be 2-sided hypothesis tests performed at the 5% level of significance. Also, all confidence intervals will be 2-sided 95% confidence intervals, unless stated otherwise. All the efficacy analyses will be performed on the assigned treatments in the double-blind phase.

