3.6 Safety Assessment

Safety data will be summarized by actual treatment received (and in total for selected analyses) in the double-blind phase based on the Safety Analysis Set.

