3.6.1 Adverse Events

An AE is any untoward medical occurrence in a clinical investigation subject administered a pharmaceutical product and that does not necessarily have a causal relationship with this treatment. All AEs are collected from the time the informed consent is signed until the subject discontinues or until Week 6 (whichever is first). All AEs will be coded to system organ class and preferred term using MedDRA version 21.0. Treatment-emergent adverse events (TEAEs) are defined as AEs that start after the first dose of study drug (lead-in infusion).

TEAEs with onset during the lead-in phase and double-blind phase will be summarized separately. TEAEs that start on or after the lead-in infusion and prior to the first double-blind infusion will be attributed to the lead-in phase, while TEAEs that start on or after the first double-blind infusion will be attributed to the double-blind phase. All AEs that start prior to the lead-in infusion will be listed.

Adverse events of special interest include the following preferred terms: hypotension, atrial fibrillation, clinically significant arrhythmia, aborted resuscitated death, and stroke.

An overview of TEAEs will be provided including counts and percentages of subjects with the following:

- Any TEAEs (overall and by maximum severity)
- Any study drug related TEAEs (overall and by maximum severity)
- Any TEAEs of special interest (overall and by maximum severity)
- Any serious TEAEs (TESAEs)
- Any TEAEs leading to discontinuation of study drug
- Any TEAEs leading to discontinuation of study
- Any TEAEs leading to death

Counts and percentages of subjects will also be presented by system organ class and preferred term for each of the categories in the overview.

Listings will be presented specifically for SAEs and TEAEs leading to discontinuation of study drug.

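### Death and hospitalization are compared on a set that requires a completed Week 6 visit, so a death before that visit cannot be counted

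*SAP*

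**What the plan says.** SAP 2.3.2 lists "Clinical Events: Death and hospitalizations" among the secondary efficacy endpoints. SAP 3.4 states "All efficacy analyses will be based on the Full Analysis Set", and 3.4.2 repeats it for this tier: "The secondary efficacy analyses will be performed on the Full Analysis Set". Section 3.4.2 then plans the incidence by arm, a 95% confidence interval for the between-arm difference based on a continuity-corrected Z-statistic, and a listing of deaths. It names no other population for this endpoint, and Section 5 (changes from the protocol) makes no exception for it.

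SAP 3.2.5 defines the Full Analysis Set (FAS) as "randomized subjects who received any blinded study drug and completed the study with Week 6 office visit".

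Two replacement rules bear on this. SAP 3.3.1: "Subjects who discontinue the study prior to the Week 6 office visit will be replaced", with the replacement drawn for the same arm. SAP 2.2.1: "Randomized subjects that have not received study drug weekly through Week 5 and returned for evaluation on Week 6 will be replaced".

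SAP 2.2.1 also provides for vital status to be collected on every subject at the end of the trial, including those who discontinued.

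**The concern.** Attending Week 6 depends on the outcome being measured. A subject who has died cannot attend, and a subject who has been hospitalized may be less likely to. Conditioning the analysis set on attendance removes every death before the visit and any hospitalization in a subject who did not come back. Replacement within the same arm then fills the gap with a subject who did complete.

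The efficacy table could therefore show no deaths before Week 6 in either arm while the safety tables of the same report show some. The error can favour either arm. If losses are equal in the two arms, the difference is right but both incidences are too low.

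**Working it through.** **Which subjects can be counted.** The argument needs only the definitions.

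1. Death and hospitalization is a secondary efficacy endpoint (2.3.2).
2. Secondary efficacy analyses use the FAS (3.4 and 3.4.2), with no exemption.
3. FAS membership needs a completed Week 6 visit (3.2.5).
4. A subject who dies before that visit fails step 3. The number of such deaths in the comparison is therefore 0 in each arm, whatever happened.
5. A completer who dies after the Week 6 visit could still be counted, because 3.4.2 sets no end of follow-up for the endpoint.

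**The plan's own figure.** The SAP gives no event rate or power for this endpoint. The only number taken from it is 18 completers per arm (2.2.1 and 3.3.1). That number agrees with 2.2.3: a two-sample t-test with difference 4.9 mmHg, SD 5 mmHg, 18 per arm and two-sided 0.05 has power 81.5%, against the stated 80%.

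**Illustration for death.** Assumptions: k subjects in one arm die after a blinded infusion and before Week 6. Each is replaced by a subject who completes. The other arm has no deaths, and nobody else is lost. The subjects who received blinded drug then number 18 + k in that arm and 18 in the other. The difference is k/(18 + k) − 0/18. The SAP gives no formula for its interval, so the usual unpooled form is assumed:

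d ± {1.96 √[p1(1 − p1)/n1 + p2(1 − p2)/n2] + ½(1/n1 + 1/n2)}

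| k | All who received blinded drug | Difference | 95% CI | Planned FAS table |
|---|---|---|---|---|
| 1 | 1/19 vs 0/18 | 5.3 points | −10.2 to 20.7 | 0/18 vs 0/18 |
| 2 | 2/20 vs 0/18 | 10.0 points | −8.4 to 28.4 | 0/18 vs 0/18 |
| 3 | 3/21 vs 0/18 | 14.3 points | −5.8 to 34.4 | 0/18 vs 0/18 |

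Exchanging the arms reverses the signs. With one death per arm, the result is 1/19 vs 1/19: difference 0, incidence 5.3% in each arm, while the FAS again shows none.

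**How likely an omitted death is.** If each of 36 subjects has an assumed risk r of dying before Week 6, the chance of at least one omitted death is 1 − (1 − r)^36. This is 30% for r = 1%, 52% for r = 2% and 84% for r = 5%.

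**Illustration for hospitalization.** Assume 2 hospitalized completers in each arm. In one arm assume 2 further subjects who are hospitalized, do not attend Week 6 and are replaced. All who received blinded drug: 4/20 − 2/18 = 20.0% − 11.1% = 8.9 points (−19.2 to 36.9). The FAS shows 2/18 vs 2/18, a difference of 0.

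**The case against.** The strongest reply is that nothing is hidden. SAP 3.6 says "Safety data will be summarized by actual treatment received" on the Safety Analysis Set, which does not require Week 6, and 3.6.1 tabulates "Any TEAEs leading to death" and serious events. Section 3.3.1 summarizes reasons for discontinuation by arm, and 3.4.2 adds a listing of deaths. This stands. A reader might infer that early deaths vanish from the report, and the SAP does not support that. But none of these outputs gives the between-arm difference with its interval. The safety tables go by treatment received rather than assigned, hospitalizations are not tabulated there as such, and the listing names no analysis set.

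A reader might also infer that every replaced subject drops out of the FAS. That goes too far. The rule in 2.2.1 also replaces subjects who missed infusions, whereas 3.2.5 asks only for any blinded drug and the Week 6 visit. A subject hospitalized for a time who misses an infusion but returns at Week 6 may be replaced and still be counted. The hospitalization illustration therefore holds only for subjects who also missed Week 6.

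Finally, the endpoint is secondary, no hypothesis test is specified for it, the arms are small and every event count above is assumed. That limits the weight of the point but does not make the chosen set suitable.

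**Conclusion.** The point holds. The SAP places death and hospitalization on a set from which every subject who dies before Week 6 is excluded by definition, so the only specified between-arm contrast for this endpoint cannot show such deaths. Hospitalizations are restricted to subjects who attended. This should be corrected before database lock.

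The exclusion itself rests on no assumption; its size does. With 1 to 3 deaths in one arm, the difference is 5.3 to 14.3 points instead of 0. All corrected intervals in the illustrations include zero, so the change is in the reported incidence and difference, not in a conclusion about significance. It would be wrong to infer from this point that the primary PCWP result is affected, or that the comparison necessarily favours levosimendan: the direction depends on which arm loses subjects.

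**What to change.** In SAP 3.4.2, add:

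> *Death and hospitalization will be analysed in all randomized subjects who received any blinded study drug, including subjects later replaced, by assigned arm. Events will be counted from the first double-blind infusion, irrespective of attendance at Week 6. The same analysis on the Full Analysis Set will be supportive.*

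Three details go with it:

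- **Death.** Use the vital status that 2.2.1 already collects. That section does not mention dates of death, so confirm that they are recorded.
- **Cut-off, if one is used.** Section 3.1.3 leaves the Visit 6 window open after Day 33, and 3.2.6 allows for visits rescheduled because of COVID-19. A cut-off at nominal Day 36 would drop a death on Day 40 in a subject still awaiting a delayed visit. Set it late enough to cover delayed visits, or also tabulate later deaths by arm.
- **Hospitalization.** Section 2.2.1 follows subjects for 2 weeks after early termination, while 3.6.1 ends adverse event collection at discontinuation or Week 6. Reconcile the two, and footnote subjects with shorter follow-up.

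The cost is SAP wording and one population flag. There are two downsides. Denominators will differ from the other efficacy tables. Hospitalization follow-up will also be incomplete in some replaced subjects: after a last infusion on nominal Day 8 or Day 15, the 14-day contact falls on Day 22 or Day 29, which is 14 or 7 days short of nominal Day 36. The gap is longer if collection stops at discontinuation. The death correction need not wait for this. A fixed 28-day window or a different interval method would be optional and is not part of this point.

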2 STUDY OVERVIEW

2.1 Study Objectives

2.1.1 *Primary Objectives*

This study will evaluate the efficacy and safety of intermittent (weekly) levosimendan infusions in hemodynamic improvement with exercise in Pulmonary Hypertension with Heart Failure and Preserved Ejection Fraction (PH-HFpEF) subjects.

2.1.2 *Secondary Objectives*

The study will evaluate the effectiveness of intermittent (weekly) levosimendan infusions in improving the following:

- Change in Cardiac Index at rest and with exercise at Week 6
- Change in pulmonary vascular resistance (PVR) effect at rest and with exercise at Week 6
- Change in pulmonary capillary wedge pressure (PCWP) when supine and legs elevated at Week 6
- Patient global assessment (based on a six-point Likert scale) at Week 6
- Exercise duration 6-min walk test at Week 6
- Physician's Assessment of Functional Class
- Clinical Events: Death and hospitalizations
 - All cause hospitalizations
 - Hospitalizations attributed to any abnormality in cardiac and/or pulmonary status.

2.1.3 *Exploratory Objectives*

Baseline echocardiographic measurements of right ventricle (RV) and left ventricle (LV) function to predict favorable response to levosimendan therapy.

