2.2.3 Sample Size Calculation and Power Considerations

The sample size was estimated for the primary comparison of levosimendan and placebo using SAS (v9.4) for windows procedure PROC POWER.

A total of 36 randomized subjects (at 1:1 levosimendan vs. placebo) will provide 80% power to detect the difference at two-sided 0.05 level, assuming a standard deviation (SD) of 5 mmHg in PCWP and a treatment difference of ≥ 4.9 mmHg.

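### The Week 6 test of NYHA functional class, as worded, does not use the baseline class shown in the shift table; the test stays valid but is usually less efficient than one that does

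*SAP*

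**What the plan says.** Section 2.1.2 introduces the secondary objectives with "The study will evaluate the effectiveness of intermittent (weekly) levosimendan infusions in improving the following", and functional class is on that list. Section 2.3.2 names the endpoint only as "Physician's Assessment of Functional Class"; the hemodynamic endpoints on the same list are worded as changes.

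Section 3.4.2 deals with the endpoint in one paragraph. The class (I to IV) is summarised by arm "as a shift table from baseline to post-baseline time point", with percentages based on subjects who have both assessments. The test follows: "The treatment difference of physician's assessment of functional class at Week 6 will be tested using the two-sided Pearson's chi-squared test".

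Section 3.4 sets the level: "all statistical tests will be 2-sided hypothesis tests performed at the 5% level of significance". Section 2.2 fixes the numbers: subjects who do not complete "will be replaced to ensure 18 subjects have completed in each study group".

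**The concern.** The shift table shows movement within subjects. As worded, the test compares where the two arms stand at Week 6, whatever class each subject started from. If subjects enter in more than one class, part of the spread at Week 6 is carried over from entry and acts as noise in the comparison. With 18 per arm, a chance difference in entry class then moves the p-value, and a real shift visible in the table can be missed by the test beside it.

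The primary and hemodynamic endpoints and the walk test use baseline through change from baseline in the ANOVA. Functional class also has a baseline value, since the shift table needs one, but the test sentence makes no use of it. Ignoring the order of the classes is a separate, smaller loss: a rank test on Week 6 class alone would still leave baseline out.

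**Working it through.** **Inputs from the SAP.** Two-sided 5% level (3.4); 18 completers per arm (2.2); four ordered classes (3.4.2). The SAP states no power for functional class. Its only calculation, in section 2.2.3, is for PCWP: "A total of 36 randomized subjects (at 1:1 levosimendan vs. placebo) will provide 80% power to detect the difference at two-sided 0.05 level". The inputs there are an SD of 5 mmHg and a difference between arms of at least 4.9 mmHg.

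**The plan's own figure.** For a two-sample t-test with 18 per arm, the noncentrality is 4.9 / (5 × √(2/18)) = 2.94 on 34 df, which gives 81.5% power; 17 per arm gives 79.1%. So 36 in total is reproduced, for PCWP only.

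**Assumptions, not in the SAP.** The baseline class mix (varied below); moves of one class only; 5% worsening in both arms (not from class IV); 10% improving on placebo and 40% on levosimendan.

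**Tests compared.**
- Planned: Pearson chi-squared on arm × Week 6 class.
- Wilcoxon on Week 6 class.
- Wilcoxon on change in class.
- Stratified mean-score (CMH) test: Q = [Σₛ(Tₛ − n₁ₛȳₛ)]² / Σₛ(n₁ₛn₀ₛ/Nₛ)Sₛ², on 1 df. Here s is baseline class, Tₛ the sum of Week 6 class scores on levosimendan, ȳₛ and Sₛ² the stratum mean and variance, and n₁ₛ, n₀ₛ and Nₛ the levosimendan, placebo and total counts.

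**Power, 5,000 simulated trials per row (%).**

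| Baseline II/III/IV | Who benefits | Planned | Wilcoxon, Week 6 | Wilcoxon, change | CMH by baseline |
|---|---|---|---|---|---|
| 35/60/5 | all | 13.3 | 21.6 | 45.5 | 42.0 |
| 50/50/0 | all | 16.3 | 21.4 | 43.7 | 41.5 |
| 30/70/0 | all | 16.0 | 25.4 | 44.4 | 42.0 |
| 10/90/0 | all | 29.2 | 35.3 | 43.8 | 40.8 |
| 0/100/0 | all | 48.2 | 45.3 | 45.3 | 44.2 |
| 35/60/5 | III/IV only | 12.5 | 16.5 | 23.7 | 23.5 |
| 50/50/0 | III/IV only | 10.3 | 13.1 | 15.2 | 16.5 |
| 30/70/0 | III/IV only | 18.8 | 22.6 | 27.5 | 27.5 |

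In the III/IV-only rows, class II subjects on levosimendan improve at the placebo rate. The CMH gain over the planned test there is 23.5 − 12.5 = 11.0, 16.5 − 10.3 = 6.2 and 27.5 − 18.8 = 8.7 points.

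**Type I error.** With 10% improving in both arms, the planned test rejects in 2.3-3.1% of trials and the CMH test in 4.3-5.1%, across the five mixes.

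**Dependence on the randomisation obtained.** These figures come from 2,000 trials each, classes II/III, with the class III counts fixed.

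| Class III at baseline, placebo v levosimendan | Improving, placebo v levosimendan | Planned (%) | CMH (%) |
|---|---|---|---|
| 11 v 11 | 20% v 20% | 0.8 | 5.0 |
| 13 v 9 | 20% v 20% | 4.0 | 5.0 |
| 14 v 8 | 20% v 20% | 12.2 | 4.6 |
| 11 v 11 | 15% v 50% | 13.8 | 50.3 |
| 13 v 9 | 15% v 50% | 50.5 | 47.5 |
| 9 v 13 | 15% v 50% | 2.0 | 48.2 |

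A gap of at least 20 points between arms in the class III share arises by chance in about 19-26% of trials when baseline is mixed.

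**The case against.** **The SAP does not say that the raw class is tested.** The test sentence follows directly on the shift table. In the same section the walk test is also described as being at Week 6, yet it is assigned the primary model, whose outcome is change. This stands: testing the raw class is the plain reading, but an inference. If a test of the shift was meant, the sentence still has to say so.

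**The test may match the endpoint.** Section 2.3.2 lists the class, not its change. The word improving in section 2.1.2 also introduces the patient global assessment and the clinical events, so it does not by itself call for a change score. A descriptive shift table beside a between-arm test is no contradiction. This stands too; the point is one of efficiency.

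**The test is valid.** A reader might infer from the 14 v 8 row that the false-positive rate is inflated. It is not: averaged over randomisations it is about 3%, and chance imbalance is already counted in that figure.

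**The gain depends on favourable assumptions.** A reader might infer that using baseline doubles power or better. That is the top of the range and needs a mixed baseline with benefit in every class. The entry criteria and baseline mix are not in the SAP.

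**Different denominators.** A reader might infer that table and test use different subjects. The Full Analysis Set (3.2.5) requires the Week 6 visit, so this would arise only if a class assessment were missing. It is hypothetical.

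**Conclusion.** The point holds as one of efficiency and clarity. As worded, the test leaves out a baseline value that is collected and tabulated. It keeps its type I error, but it is usually less powerful, and for a given trial its result depends on baseline imbalance.

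Under the stated assumptions, the change from the planned test to one using baseline runs from about 13-16% to 41-45% power (mixed baseline, all can benefit), through 5-11 points (only class III/IV benefit), to no gain when all subjects share one class. In that last case the planned test was about 4 points ahead of the CMH test (48.2% v 44.2%). Where baseline is mixed and all benefit, the larger part of the gain comes from baseline, since a rank test on Week 6 class reaches only 20-25%.

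Even the better test has under 50% power in these 40% v 10% scenarios. The endpoint is secondary in a trial sized for PCWP, and the primary analysis is untouched.

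**What to change.** Replace the test sentence in section 3.4.2 with one pre-specified test:

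> The treatment difference in functional class at Week 6 will be tested with a two-sided row-mean-score Cochran-Mantel-Haenszel test stratified by baseline class, in subjects with both a baseline and a Week 6 assessment.

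State that the classes are scored as integers, as in the calculations above, and record the change in section 5. The endpoint name in section 2.3.2 can stay, because the outcome is still the Week 6 class. The same edit makes use of the order of the classes and puts the test in the same subjects as the Week 6 shift table.

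The cost is a sentence or two of SAP wording before database lock, with no new data. The downside is that subjects without a baseline class, or in a baseline stratum with nobody from the other arm (including anyone alone in a stratum), do not contribute.

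### With no events in either arm, the planned continuity-corrected Z interval for death and hospitalization shrinks to ±5.6 points at 18 per arm, about a third of what a score interval gives

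*SAP*

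**What the plan says.** Section 3.4.2 summarizes the incidence of death and hospitalization by arm and adds an interval for the difference: "Two-sided 95% CIs for the observed difference in clinical events: death and hospitalizations between the treatment groups" "will be presented based on a continuity-correct Z-statistic". It gives no formula, no exact or score alternative, and no rule for zero or sparse counts.

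The analysis set is stated in the same section: "The secondary efficacy analyses will be performed on the Full Analysis Set". Section 3.2.5 defines that set as "randomized subjects who received any blinded study drug and completed the study with Week 6 office visit".

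The number per arm comes from section 3.3.1, where dropouts are replaced "to ensure 18 randomized subjects in both arms (levosimendan, placebo) have completed the study for the primary analysis". The SAP gives no expected rate for either event.

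**The concern.** A Z interval takes its width from the observed proportions. With 18 subjects per arm followed for about five weeks, no event in either arm is a plausible result for hospitalization. For death it is the expected one, because a subject who dies before the Week 6 visit cannot be in the Full Analysis Set. In that situation the estimated variance is zero, and the printed interval reflects only the continuity correction. A study report showing a difference of 0 with limits of ±5.6 points could be taken to mean that larger excesses are incompatible with the data. Eighteen subjects per arm cannot support that.

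**Working it through.** **Inputs.** n = 18 per arm (section 3.3.1); two-sided 95%, z = 1.96 (section 3.4.2). Event rates are not in the SAP and are assumed here over 0-25% per arm. The Wald form is also an assumption, as no formula is given.

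**The plan's own figure.** The SAP states no figure for this interval. Its sample size claim in section 2.2.3 is "A total of 36 randomized subjects (at 1:1 levosimendan vs. placebo) will provide 80% power", "assuming a standard deviation (SD) of 5 mmHg in PCWP and a treatment difference of ≥ 4.9 mmHg". A two-sample t-test with these inputs has 81.5% power at 18 per arm and 79.1% at 17, so 18 per arm is consistent with the stated 80%.

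**Step 1, the planned interval.**
(p1 − p2) ± [1.96 × √(p1(1−p1)/18 + p2(1−p2)/18) + ½(1/18 + 1/18)]

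**Step 2, no events.** With p1 = p2 = 0 the square root is 0, and the half-width is ½(1/18 + 1/18) = 1/18 = 5.6 points. A pooled variance gives the same result. No event rate has to be assumed.

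**Step 3, what the data support.** The Wilson upper limit for 0/18 is z²/(n + z²) = 3.84/21.84 = 17.6%. The Newcombe interval for 0/18 vs 0/18 is therefore ±17.6 points; Miettinen-Nurminen gives ±18.0. The exact (Clopper-Pearson) upper limit for a single arm is 1 − 0.025^(1/18) = 18.5%. The planned width is 5.6/17.6, about one third.

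**Step 4, once events occur (points).**

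| Events | Planned | Newcombe |
|---|---|---|
| 0 vs 0 | −5.6 to +5.6 | −17.6 to +17.6 |
| 1 vs 0 | −10.6 to +21.7 | −12.6 to +25.8 |
| 1 vs 1 | −20.5 to +20.5 | −20.7 to +20.7 |
| 2 vs 0 | −9.0 to +31.2 | −8.2 to +32.8 |
| 2 vs 1 | −18.0 to +29.1 | −16.2 to +27.7 |

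The gap is large at 0 vs 0, modest at 1 vs 0 and small after that.

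**Step 5, coverage by enumeration of all 19 × 19 outcomes.** The chance of no events in either arm is (1−p1)^18 × (1−p2)^18.

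| Assumed true rates | Planned coverage | Miss rate | Chance of 0 vs 0 | Newcombe coverage |
|---|---|---|---|---|
| 6% vs 0% | 67.1% | 32.9% | 32.8% | over 99.9% |
| 8% vs 1% | 81.4% | 18.6% | 18.6% | 99.8% |
| 10% vs 0% | 84.9% | 15.1% | 15.0% | 99.9% |
| 10% vs 1% | 87.2% | 12.8% | 12.5% | 99.7% |
| 5% vs 0% | over 99.9% | under 0.1% | 39.7% | over 99.9% |
| 5% vs 5% | 99.9% | 0.1% | 15.8% | 99.1% |
| 10% vs 5% | 99.6% | 0.4% | 6.0% | 98.8% |
| 15% vs 5% | 96.1% | 3.9% | 2.1% | 98.0% |

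In the four poor rows the miss rate is almost exactly the chance of 0 vs 0. It appears only when the true difference exceeds 5.6 points: 6% vs 1%, which differs by 5 points, is covered over 99.9% of the time. On a 1-point grid of rates from 0 to 25% (351 pairs), planned coverage is below 95% in 46 pairs and below 90% in 17. The lowest coverage is 67.1%, against 94.7% for Newcombe and 94.3% for Miettinen-Nurminen.

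**The case against.** Several objections stand and limit the point.

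- The under-coverage is not a second defect. It is the 0 vs 0 outcome seen from another side, and it needs particular rates: one arm near zero and the other several points higher. In 305 of the 351 assumed pairs, coverage is at least 95%.
- A reader might infer that the planned interval is wrong for rare events in general, or too wide when the rates are equal. The figures do not support this. The 1 vs 1, 2 vs 0 and 2 vs 1 intervals nearly match Newcombe, and at 5% vs 5% both methods cover above 99%.
- The Wald form is inferred. An interval obtained by inverting a score-type test would not collapse. The SAP does not name one, so even if that was intended the text should say so.
- A reader might infer that the SAP uses this interval to exclude harm. It does not: no test, margin or decision is attached to it. Incidence by arm and a listing of deaths appear beside it, and section 3.6.1 reports serious events and events leading to death on the Safety Analysis Set.

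None of this removes the collapse at zero events, for which section 3.4.2 has no provision.

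**Conclusion.** The point holds in a narrow form. Under the usual Wald reading, 0/18 vs 0/18 gives ±5.6 points where score intervals give ±17.6 to ±18.0. That part is algebra and depends only on the assumed form and n = 18. The fall in coverage to roughly 67-87% depends on assumed rates, with one arm near 0-1%, the other about 6-10%, and a true difference above 5.6 points. Elsewhere the planned interval is adequate or conservative.

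A reader might also infer that a better interval would by itself repair the death comparison. It would not: with the Week 6 visit required for the Full Analysis Set, deaths before that visit are zero by construction, and any interval would describe structural zeros. The consequence is minor. It affects one secondary endpoint, and neither the primary analysis nor the sample size is touched.

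**What to change.** In section 3.4.2, replace the continuity-corrected Z interval with a named score interval for the risk difference, Miettinen-Nurminen or Newcombe, for death and for hospitalization. In the same paragraph, set the population for these two events to all randomized subjects who received any blinded study drug, by assigned arm, in place of the Full Analysis Set.

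The cost is two sentences of SAP text and a standard SAS option. Intervals become wider when there are no events (±17.6 to ±18.0 points instead of ±5.6). Denominators may exceed 18 per arm because replaced subjects stay in. Subjects who stop early will have different follow-up, which the table should state. For death the data should exist, since section 2.2.1 collects vital status for every subject at the end of the trial.
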